1. PROTOCOL SUMMARY

Objective(s)	To demonstrate safety and effectiveness of lumen-apposing metal stents for resolution of walled off pancreatic necrosis (WONs) in patients with WONs with solid component >30%
Test Device	AXIOS™ Stent and Electrocautery Enhanced Delivery System
Control Device	None
Study Design	Prospective, single arm, multi-center trial
Planned Number of Subjects	40
Planned Number of Investigational Sites	Up to 6 centers
Primary Endpoints	
Primary Effectiveness Endpoint:
 
Resolution of WON with endoscopic drainage defined as radiographic decrease of WON size to ≤ 3cm evaluated by CT scan or MRI
 
Primary Safety Endpoint:
 
AXIOS™ stent related or WON drainage procedure related serious adverse events

Additional Endpoints	
 Reduction of WON-related clinical symptoms. Note: WON-related symptoms as defined in Inclusion Criteria #4 in the protocol Technical AXIOS™ stent placement success, defined as placement in desired location using endoscopic/EUS techniques per standard of practice. Technical AXIOS™ stent removal success, defined as ability to remove the AXIOS™ stent using an endoscopic snare or forceps or graspers without AXIOS™ stent removal related serious adverse events. Drainage procedural time: Time elapsed between initial puncture of the WON with electrocautery to endoscope retrieval. Resolution of WON with or without necrosectomy by 6 months post AXIOS™ stent removal. Time to WON resolution using same definition as for primary endpoint, namely:

	
 • Resolution of WON with endoscopic drainage defined as radiographic decrease of WON size to ≤ 3cm evaluated by CT scan or MRI 
7. Recurrence of WON after initial resolution and up to 6 months post AXIOS™ stent removal.
 
8. Stent lumen patency, evaluated via imaging or direct visual inspection with endoscope, and defined as one or both of the following:
 
 • Drainage through AXIOS™ stent visualized from the stomach or bowel, and/or • Visual confirmation of AXIOS™ stent lumen patency 
9. Fluoroscopy (time) per endoscopic procedure.
 
10. Incidence of new organ failure from drainage procedure to WON resolution.
 
11. Change in Quality of Life score (SF-12 questionnaire) from baseline to stent removal and end of study


Primary Effectiveness Endpoint Assessment
	
Note: Success will be based on the number of WONs resolved, not on the number of AXIOS™ Stents required to achieve resolution.
 
 • If it is determined that the fluid collection is actually two separate collections, and each collection is drained via an AXIOS™ stent, then each collection will be assessed individually via the drainage success criteria of ≤ 3cm. • If it is determined that the fluid collection is a single collection but the drainage is inadequate via a single AXIOS™ stent, then the success of the AXIOS™ drainage will be assessed as follows: 
 ○ If a second AXIOS™ stent is used at a new drainage site/original drainage site and the entire fluid collection is drained to meet the success criteria of ≤ 3cm then the collection will be considered to be a single collection drainage success. ○ If a second AXIOS™ stent is used at a new drainage site and the entire fluid collection does not drain adequately to meet the drainage success criteria of ≤ 3cm then the fluid drainage of the collection will be considered to be a single drainage failure. ○ If a plastic stent is used at a new drainage site and the entire fluid collection drains to meet the drainage success criteria of ≤ 3cm then the fluid drainage will be considered indeterminate. ○ If a plastic stent is used at a new drainage site and the entire fluid collection does not drain to meet the drainage success criteria of ≤ 3cm then the fluid drainage will be considered a single drainage failure.

2. INTRODUCTION

This statistical plan addresses the planned analyses for the Axios WON Drainage IDE Study based on protocol # 92153943. Specified analyses may be used for scientific presentations and/or manuscripts and may not all be provided to Regulatory Authorities.

3. ENDPOINT ANALYSIS

3.1 Primary Effectiveness Endpoint

The primary effectiveness endpoint for this study is the resolution of WON with endoscopic drainage defined as radiographic decrease of WON size to ≤ 3 cm evaluated by CT scan or MRI.

Primary Effectiveness Endpoint Assessment:

Note: Success will be based on the number of WONs resolved, not on the number of AXIOS™ Stents required to achieve resolution.

- If it is determined that the fluid collection is actually two separate collections, and each collection is drained via an AXIOS™ stent, then each collection will be assessed individually via the drainage success criteria of ≤ 3 cm.
- If it is determined that the fluid collection is a single collection but the drainage is inadequate via a single AXIOS™ stent, then the success of the AXIOS™ drainage will be assessed as follows:
 - If a second AXIOS™ stent is used at a new drainage site/original drainage site and the entire fluid collection is drained to meet the success criteria of ≤ 3 cm then the collection will be considered to be a single collection drainage success.
 - If a second AXIOS™ stent is used at a new drainage site and the entire fluid collection does not drain adequately to meet the drainage success criteria of ≤ 3 cm then the fluid drainage of the collection will be considered to be a single drainage failure.
 - If a plastic stent is used at a new drainage site and the entire fluid collection drains to meet the drainage success criteria of ≤ 3 cm then the fluid drainage will be considered indeterminate.
 - If a plastic stent is used at a new drainage site and the entire fluid collection does not drain to meet the drainage success criteria of ≤ 3 cm then the fluid drainage will be considered a single drainage failure.

3.1.1 Hypothesis

As in the original IDE, #G130264, there is no formal statistical hypothesis for this study. The proportion of AXIOS patients with reduction of WON size to ≤ 3 cm within 60 days from AXIOS™ stent placement in the original IDE is 76.7% (23/30) [95% CI (57.7%, 90.0%)] patients. Given that the WONs in the proposed IDE will have an estimated necrotic material content above 30%, namely larger than in IDE #G130264, a slightly lower success rate of 70% is expected in this study. This success rate is within the range of reported WON resolution rates in several recent publications [1-7] representing 448 patients for which a random effects meta-analysis yields a mid-point WON resolution rate of 67.0% [95% CI (60.0%, 73.4%)] for WON

drainage with plastic stents (Table 1), an established WON drainage method as described in the ASGE guidelines on treatment of pancreatic fluid collections [8].

Table 1. Plastic Stent WON Resolution Rates from Recent Publications [1-7]

Study	% Resolution (x/N)	95% Confidence Interval
Bapaye (2017)	73.8% (45/61)	(60.9%, 84.2%)
Gardner et al (2009)	68.9% (31/45)	(53.4%, 81.8%)
Papachristou (2007)	52.8% (28/53)	(38.6%, 66.7%)
Schmidt (2015)	61.7% (50/81)	(50.3%, 72.3%)
Smoczynski (2015)	75.9% (85/112)	(66.9%, 83.5%)
Abu [name] (2017)	75.0% (27/36)	(57.8%, 87.9%)
Varadarajulu (2011)	60.0% (36/60)	(46.5%, 72.4%)
Random-Effects Meta-Analysis	67.0%	(60.0%, 73.4%)

3.1.2 Analysis

The primary effectiveness endpoint will be summarized as the proportion of patients who have resolution of WON with endoscopic drainage defined as radiographic decrease of WON size to ≤ 3 cm evaluated by CT scan or MRI out of all patients who have an AXIOS™ stent successfully implanted. A Clopper-Pearson exact 95% confidence interval will also be calculated.

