**Table 7.1 Plastic Stent WON Resolution Rates from Recent Publications**

Study	% Resolution (x/N)	95% Confidence Interval
Bapaye (2017)	73.8% (45/61)	(60.9%, 84.2%)
Gardner et al (2009)	68.9% (31/45)	(53.4%, 81.8%)
Papachristou (2007)	52.8% (28/53)	(38.6%, 66.7%)
Schmidt (2015)	61.7% (50/81)	(50.3%, 72.3%)
Smoczynski (2015)	75.9% (85/112)	(66.9%, 83.5%)
Abu [name] (2017)	75.0% (27/36)	(57.8%, 87.9%)
Varadarajulu (2011)	60.0% (36/60)	(46.5%, 72.4%)
Random-Effects Meta-Analysis	67.0%	(60.0%, 73.4%)

Statistical Methods:

The primary effectiveness endpoint will be summarized as the proportion of patients who have resolution of WON with endoscopic drainage defined as radiographic decrease of WON size to  $\leq 3$ cm evaluated by CT scan or MRI out of all patients who have an AXIOS™ stent successfully implanted. A Clopper-Pearson exact 95% confidence interval will also be calculated.

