## **14 Potential Risks and Benefits**

### **14.1 *Anticipated Adverse Device Effects***

Possible Adverse Events associated with the use of the AXIOS™ Stent and Electrocautery-Enhanced Delivery System may include those often associated with any endoscopic procedure. These complications include:

- Anesthesia complications
- Improper AXIOS Stent placement; incomplete deployment; stent migration into the fluid collection or, GI tract; separation of coating material from stent; stent fracture; coating material wear; coating material failure; puncture of coating material
- Tissue ingrowth or overgrowth leading to difficulty or a failure to remove stent
- Stent dislodgement
- Adverse reaction to implant materials and/or delivery system (e.g., abdominal or back pain, nausea, infection, fever, chronic inflammation or foreign body reaction)
- Minor or excessive bleeding requiring intervention
- Leakage of fluid collection or bowel contents causing inflammation or peritonitis
- Stent occlusion
- Local infection at the implant site
- Tissue damage during stent implantation and/or removal
- Ulceration or erosion of mucosal or organ wall linings
- Pneumoperitoneum
- Sepsis (bacterial, endotoxin or fungal)
- Perforation
- Surgical intervention (endoscopy, transfusion or surgery)
- Persistent connection to the fluid collection after removal (fistula)
- Unintended electrical shock, muscle stimulation or burns
- Cardiac arrhythmia or arrest
- Death

Please refer to the Investigator Brochure for a list of anticipated adverse device effects.

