3.2.2 Analysis

The primary safety endpoint will be summarized as the proportion of patients who have AXIOS™ stent related or WON drainage procedure related serious adverse events out of all patients who have an AXIOS stent successfully implanted. A Clopper-Pearson exact 95% confidence interval will also be calculated.

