4.2 Analysis Sets

Enrolled Cohort - A subject will be considered enrolled when the ICF is signed.

Intent-to-treat Cohort - The ITT cohort is defined as all subjects who signed the ICF, were evaluated for inclusion/exclusion criteria, and in whom the endoscopic procedure was initiated.

Treated Cohort - The treated cohort is defined as all ITT subjects who have an AXIOS™ stent implanted for the purpose of WON drainage. Subjects in the treated cohort will be counted towards the enrollment ceiling and this cohort will be considered the primary analysis cohort.

Per Protocol Cohort - The PP cohort is defined as all treated subjects for whom an AXIOS™ stent was implanted for the purpose of WON drainage and met all eligibility criteria.

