5. ADDITIONAL DATA ANALYSES

5.1 Additional Endpoints

1. Reduction of WON-related clinical symptoms. *Note: WON-related symptoms as defined in Inclusion Criteria #4 of the protocol.*
2. Technical AXIOS™ stent placement success, defined as placement in desired location using endoscopic/EUS techniques per standard of practice.
3. Technical AXIOS™ stent removal success, defined as ability to remove the AXIOS™ stent using an endoscopic snare or forceps or graspers without AXIOS™ stent removal related serious adverse events.
4. Drainage procedural time: Time elapsed between initial puncture of the WON with electrocautery to endoscope retrieval.
5. Resolution of WON with or without necrosectomy by 6 months post AXIOS™ stent removal.
6. Time to WON resolution using same definition as for primary endpoint, namely:
 - Resolution of WON with endoscopic drainage defined as radiographic decrease of WON size to ≤ 3 cm evaluated by CT scan or MRI.
7. Recurrence of WON after initial resolution and up to 6 months post AXIOS™ stent removal.
8. Stent lumen patency, evaluated via imaging or direct visual inspection with endoscope, and defined as one or both of the following:
 - Drainage through AXIOS™ stent visualized from the stomach or bowel, and/or
 - Visual confirmation of AXIOS™ stent lumen patency
9. Fluoroscopy (time) per endoscopic procedure.
10. Incidence of new organ failure from drainage procedure to WON resolution.
11. Change in Quality of life score (SF-12 questionnaire) from baseline to stent removal and end of study

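### Both primary rates are divided by patients with a stent *successfully* implanted, an undefined set that need not match the declared primary cohort

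*SAP*

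**What the plan says.** SAP 4.2 defines the cohort by implantation alone: "The treated cohort is defined as all ITT subjects who have an AXIOS™ stent implanted for the purpose of WON drainage". It then gives that cohort two roles: "Subjects in the treated cohort will be counted towards the enrollment ceiling and this cohort will be considered the primary analysis cohort". Protocol 5.5 says the same.

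The analysis rules use another set. SAP 3.1.2 takes the effectiveness count "out of all patients who have an AXIOS™ stent successfully implanted" and SAP 3.2.2 divides the safety count by "patients who have an AXIOS stent successfully implanted". The Statistical Methods paragraphs of Protocol 7.1 and 7.2 carry the same wording. The success criteria in SAP 3.3.1 and 3.3.2 use a third term, AXIOS patients, which is not defined either.

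The nearest thing to a definition of successful placement is additional endpoint 2 in SAP 5.1: "Technical AXIOS™ stent placement success, defined as placement in desired location using endoscopic/EUS techniques per standard of practice". No section ties it to the primary denominators. Protocol 14.1 lists among possible events "Improper AXIOS Stent placement; incomplete deployment; stent migration into the fluid collection or, GI tract".

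**The concern.** The extra word *successfully* either means nothing or removes someone. If it removes someone, the candidate is a patient who received an AXIOS stent that ended up in the wrong place and who never had a well-placed one. That patient fills one of the 40 places and belongs to the primary cohort, but would be missing from the numerator and denominator of both primary rates.

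Such patients plausibly have more drainage failures and more procedural harm, so leaving them out would condition both endpoints on an early device success. The plan has no hypothesis test, so the verdict rests on the observed proportion alone, and who is in the denominator is part of the decision rule. In an open single-arm study, an undefined denominator can be settled after the outcomes are known. The point concerns patients who did receive a stent, not procedures that ended with no implant.

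**Working it through.** **Inputs.** Safety limit: observed rate at most 17.5% (SAP 3.3.2). Effectiveness limit: observed rate at least 67% (SAP 3.3.1). Size: 40 (SAP 3.3), with Protocol 4.4 allowing up to 40 treated. Related-SAE rates: 10.0% (3/30) expected and 16.7% as the plastic-stent benchmark (SAP 3.2.1). The documents give no number of misplaced stents; one or two is assumed.

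**The plan's own figures.** The 40 has no statistical derivation to reproduce. The benchmarks do reproduce. A DerSimonian-Laird random-effects model on the logit scale, with y = ln(x/(n − x)), v = 1/x + 1/(n − x) and weights 1/(v + τ²), gives 67.0% (60.0%, 73.4%) from SAP Table 1 and 16.7% (10.1%, 26.3%) from SAP Table 2, as stated. The safety limit is 0.175 × 40 = 7.0, so 7/40 lies exactly on it.

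**Limits as counts.** Safety passes if x ≤ 0.175n; effectiveness passes if r ≥ 0.67n.

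| n | 0.175n | most SAE patients | 0.67n | fewest resolved |
|---|---|---|---|---|
| 40 | 7.00 | 7 | 26.80 | 27 |
| 39 | 6.825 | 6 | 26.13 | 27 |
| 38 | 6.65 | 6 | 25.46 | 26 |

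**Effect of exclusion.** With N treated and k excluded, of whom s count in the numerator, x/N becomes (x − s)/(N − k).

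| Treated | Excluded | All treated | After exclusion |
|---|---|---|---|
| 40 | 1, no related SAE | 7/40 = 17.50%, pass | 7/39 = 17.95%, fail |
| 40 | 1, related SAE | 8/40 = 20.00%, fail | 7/39 = 17.95%, fail |
| 40 | 2, both related SAE | 8/40 = 20.00%, fail | 6/38 = 15.79%, pass |
| 39 | 1, related SAE | 7/39 = 17.95%, fail | 6/38 = 15.79%, pass |
| 40 | 1, resolved | 27/40 = 67.50%, pass | 26/39 = 66.67%, fail |
| 40 | 1, not resolved | 26/40 = 65.00%, fail | 26/39 = 66.67%, fail |
| 40 | 2, neither resolved | 26/40 = 65.00%, fail | 26/38 = 68.42%, pass |
| 39 | 1, not resolved | 26/39 = 66.67%, fail | 26/38 = 68.42%, pass |

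With 39 treated, one patient who has a related SAE and does not resolve can therefore move both endpoints from fail to pass.

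**How often at 40.** Assume exactly one exclusion, independent of SAE status. The safety verdict changes only if the other 39 patients include exactly 7 with an event and the excluded patient has none: (1 − p) × P(7 of 39).

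- p = 10%: 0.90 × 0.0528 = 4.8%. The chance of meeting the limit falls from 95.8% (at most 7 of 40) to 91.1% (at most 6 of 39).
- p = 16.7%: 0.833 × 0.1609 = 13.4%. The chance falls from 65.1% to 51.7%.

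**The case against.** The strongest reply is that *successfully implanted* merely paraphrases the treated cohort: patients who received a stent, as opposed to ITT patients in whom the procedure was only started. SAP 4.2 names that cohort as primary, and additional endpoint 2 is a separate outcome. This is a fair reading. A reader might infer that the plan actually excludes misplaced-stent patients, but no section says so.

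Three further limits stand. Endpoint 2 speaks of location only, so even if it were borrowed as the definition it would not reach an incompletely deployed stent. The denominator is worded by patient, and SAP 3.1 disregards the number of AXIOS stents used, so a patient rescued with a well-placed AXIOS stent stays in. And Protocol 14.1 lists what may happen, without frequencies.

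The plan also offers some transparency: placement success is reported separately, and descriptive statistics cover ITT and treated patients (SAP 4.1), so misplacements and their SAEs should be visible. But visibility does not settle which denominator carries the verdict. If the terms are synonyms, removing the word loses nothing; if they are not, the analysis rule conflicts with the declared cohort.

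**Conclusion.** The conflict is one of wording, present in both documents, and it bears on both success criteria. It should be resolved before analysis. Whether any patient would be excluded depends on how an undefined word is read and on at least one patient having a misplaced stent and no successful AXIOS placement.

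The size is limited to results near the limits. A reader might infer that dropping one patient with an SAE could rescue a failed safety result at the planned size. It cannot: with 40 treated, a single exclusion can only turn a safety pass into a fail, and the same holds for effectiveness. A change in the device's favour needs two exclusions at 40 treated, or a smaller treated total such as 39, which Protocol 4.4 permits. The 4.8% and 13.4% are conditional on one exclusion occurring independently of SAE status; they are not overall probabilities.

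Nor should 26/39 be read as meeting 67% by whole-number rounding. No such rule is given, the documents report observed rates to one decimal, and 66.7% is below 67%.

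**What to change.** In SAP 3.1.2 and 3.2.2 and in Protocol 7.1 and 7.2, replace the denominator phrase with: all patients in the treated cohort. Add one sentence stating that any patient in whom an AXIOS stent was deployed counts, whether or not it was in the desired location and whether or not it was removed during the same procedure. Apply the 67% and 17.5% criteria to that unrounded proportion, and use the same term in SAP 3.3.1 and 3.3.2 in place of AXIOS patients.

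The cost is one phrase in four places plus a sentence, with no new data. The downside is that the reported rates may be slightly less favourable.

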3.2 Primary Safety Endpoint

The primary safety endpoint is AXIOS™ stent related or WON drainage related serious adverse events for AXIOS subjects.

3.2.1 Hypothesis

As in the original IDE, #G130264, there is no formal statistical hypothesis for this study. The proportion of AXIOS patients with AXIOS™ stent related or WON drainage procedure related serious adverse events in the original IDE is 10.0% (3/30) [95% CI (2.1%, 26.5%)] patients. A similar rate of AXIOS™ stent related or WON drainage procedure related serious adverse events is expected in this study. This event rate is within the range of reported stent related or WON drainage procedure related serious adverse event rates in several recent publications [2-4, 9] representing 306 patients for which a random effects meta-analysis yields a mid-point related SAE rate of 16.7% [95% CI (10.1%, 26.3%)] for WON drainage with plastic stents (see Table 2 and Table 3 (categorized events from Table 2)), an established WON drainage method as described in the ASGE guidelines on treatment of pancreatic fluid collections [8].

Table 2. Plastic Stent-related or WON Drainage-procedure related Serious Adverse Events Rates from Recent Publications [2-4, 9]

Study	% Related SAEs (x/N)	95% Confidence Interval
Papachristou (2007)	20.8% (11/53)	(10.8%, 34.1%)
Schmidt (2015)	12.3% (10/81)	(6.1%, 21.5%)
Smoczynski (2015)	25.9% (29/112)	(18.1%, 35.0%)

Study	% Related SAEs (x/N)	95% Confidence Interval
Varadarajulu (2011)	8.3% (5/60)	(2.8%, 18.4%)
Random-Effect Meta-Analysis	16.7%	(10.1%, 26.3%)

Table 3. Categorized Plastic Stent-related or WON Drainage-procedure related Serious Adverse Events Rates from Recent Publications [2-4, 9]

SAE	% (x/N)
Bleeding	11.1% (34/306)
Perforation	2.6% (8/306) [5 GI; 2 Collections; 1 Undefined]
Pneumoperitoneum	1.3% (4/306)
Sepsis	0.7% (2/306)*
Stent migration	1.0% (3/306)
Multiple organ failure	1.0% (3/306)
Other - loss of access to the collection (due to hypertension)	0.3% (1/306)

*Note: 1 patient with septic shock also had multiple organ failure (death)

3.2.2 Analysis

The primary safety endpoint will be summarized as the proportion of patients who have AXIOS™ stent related or WON drainage procedure related serious adverse events out of all patients who have an AXIOS stent successfully implanted. A Clopper-Pearson exact 95% confidence interval will also be calculated.

3.3 Sample Size and Success Criteria

The WON resolution rates and related SAE rates reported in the above provided study references are similar to those reported for WON drainage using plastic stents in a recent systematic review and meta-analysis comparing plastic stents to metal stents, including lumen-apposing metal stents (LAMS) for the management of WONs [10]. Appendix I in Section 21 of the protocol provides a few key points from this systematic review.

Although reported effectiveness and safety event rates from different sources appear similar, 95% confidence intervals are fairly wide, mostly due to small sample sizes and heterogeneity in WONs and in detailed procedural WON drainage steps. Therefore we chose to increase the sample size of the present study to be slightly larger than in the original IDE study #G130264, which was 30 patients.

We will conduct the present study in 40 patients.

3.3.1 Effectiveness Endpoint Success Criteria

An observed rate of 67% or higher for the proportion of AXIOS patients with reduction of WON size to ≤ 3 cm within 60 days from AXIOS™ stent placement is required for success.

This rate is the same as the point estimate of the random-effect meta-analysis of WON resolution rates for plastic stents provided in Table 1. Note that in the recent systematic review and meta-

analysis [10] (Appendix I in Section 21 of the protocol) WON resolution rates were higher and the number of procedures required to reach WON resolution were lower when using LAMS compared to plastic stents for WON drainage. Thus, the proposed success criteria for effectiveness seems reasonable.

